## 11.2. Description of the Statistical Methods

#### **Exposures**

The primary exposure will be use of the Hypertension Plus monitoring system, defined by SNOMED codes recorded in the clinical system compared to no use. The date on which the patients started using the system ("Time 0") will be extracted and patients will be classified as exposed from this date onwards. These patients will be classified as unexposed prior to this date. Where a practice or individual stops using the system, this will be classed as the end of exposure. Patients who never use the system will form the unexposed group.

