#### Covariates

Covariates will be any factors that may confound the relationship between use of the Hypertension Plus system and the primary outcome which have been identified from our previous research. These are:

- Age (years)
- Gender
- Ethnicity (White, Black, Asian, Mixed, Other)
- Smoking status (current, ex or non)
- Index of Multiple Deprivation
- Body mass index (kg/m^2)
- Total cholesterol (mmol/L)
- Systolic and diastolic blood pressure (clinic or home readings)
- Past medical history:
  - Diagnosis of diabetes (Type 1 or 2)
  - Previous myocardial infarction or stroke
  - Diagnosis of chronic kidney disease
  - Estimated glomerular filtration rate (eGFR, ml/min/1.73 m^2)
- Medication use:
  - Statin treatment (drug type and dose)
  - o Antihypertensive medication use (drug type and dose, defined daily dose)
  - o Other current cardiovascular medication
- Electronic Frailty Index and/or characteristics making up the electronic frailty index
- Health Economic Resource use including consultation rate, timing, personnel undertaking, referrals and admissions.

Covariates will be defined using the closest available electronic healthcare records data prior to "Time 0" for all patients, but within the previous two years. Otherwise this data will be regarded as missing.

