## Statistical modelling

Multilevel models and Difference-in-Differences (DiD) analysis will be used to describe changes in outcomes over time (12 months before and after "Time 0") and the effect of the introduction of the Hypertension Plus system. Difference-in-differences (DiD) allows comparison of differences in outcomes, TM101-A

Protocol Template for a Research Study\_version 15.0 CONFIDENTIAL
© Copyright: The University of Oxford and Oxford University Hospitals NHS Foundation Trust 2019 Page 18 of
28

before and after an intervention, between groups. Bias from unobserved fixed variables within each group is automatically accounted for in this type of analysis but bias from variables that affect allocation to the exposed an unexposed group must still be accounted for.

• Primary outcome (SBP) and secondary DBP outcome:

For the primary outcome (SBP) and secondary outcome of DBP, multilevel linear models will be used to model these outcomes over time, including a fixed linear effect for time relative to "Time 0" and random effects for patient and practice level average BP. The models will also include as fixed effects, an indicator for whether each BP was measured in the clinic or at home, an indicator for exposure and, to estimate difference-in-differences, interaction terms between the exposure and time period variable (initial model).

The addition of random effects for patient and practice level trends into the initial model will be considered by comparing models via the likelihood ratio test and Akaike Information Criterion (AIC), with terms retained if model fit is significant improved or the AIC is lower. Covariates will be included as fixed effects without selection once the initial model is finalised. To account for autocorrelation between BP measurements in the same individual, standard errors will be estimated using robust methods and more specifically the Huber-White Sandwich estimator of the variance which can adjust for within-cluster correlation.

The effect of the Hypertension Plus intervention at 6 and 12 months will be estimated by comparing the estimated BP values in the exposed at unexposed groups at these time points, as derived from the models. These estimates, and estimates from the models will be summarised in tables including p-values and 95% confidence intervals.

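### As written, the baseline covariates do not adjust the difference-in-differences term for confounding of change in blood pressure

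*Protocol*

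**What the plan says.** Section 11.2, Covariates, gives the purpose of the list: "Covariates will be any factors that may confound the relationship between use of the Hypertension Plus system and the primary outcome". It also fixes the timing: "Covariates will be defined using the closest available electronic healthcare records data prior to" Time 0, looking back at most two years. Each covariate is therefore one constant per patient. The list covers age, ethnicity, deprivation, comorbidity, treatment, frailty and resource use, and also "Systolic and diastolic blood pressure (clinic or home readings").

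Section 11.2, Statistical modelling, notes that differencing removes fixed unobserved differences but warns that "bias from variables that affect allocation to the exposed an unexposed group must still be accounted for". The initial model for systolic and diastolic pressure has linear time, random intercepts for patient and practice, a clinic/home indicator, an exposure indicator and, "to estimate difference-in-differences, interaction terms between the exposure and time period variable (initial model"). The covariates are then handled in one sentence: "Covariates will be included as fixed effects without selection once the initial model is finalised". No covariate-by-period or covariate-by-time term is named, and no weighting.

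Two other sentences bear on what the covariates can do. The effect at 6 and 12 months "will be estimated by comparing the estimated BP values in the exposed at unexposed groups at these time points". Under Exposures, users of the system have a changing status: "These patients will be classified as unexposed prior to this date".

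**The concern.** A covariate fixed before Time 0 and entered as a main effect raises or lowers a patient's pressure by the same amount in both periods. The exposure-by-period coefficient compares changes, so that amount has already cancelled. What confounds a comparison of changes is a covariate that predicts change in pressure and is distributed differently in users and non-users. Only a term that lets the covariate act differently before and after Time 0, or weighting or matching on it, addresses this.

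Patients choose the system together with their clinicians (section 9.4), and section 12.3 lists confounding from the non-randomised design as its first bias. Age, frailty and current treatment could plausibly affect both uptake and later pressure. An estimate reported as adjusted could then carry all of the confounding of change that the section itself says must be dealt with.

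**Working it through.** **1. The plan's own figure.** Section 11.2 gives 91% power for -3 mm Hg with 8 practices of 100 patients, 25% exposed, four readings per patient, SDs of 5 (practice), 17 (patient) and 10 mm Hg (reading), and a 5% level, taken here as two-sided. Simulation of 1000 datasets with random reading times gave 89.6% for the full difference-in-differences model and 92.5% without a period main effect. In closed form, with two readings before and two after, the change has variance 100/2 + 100/2 = 100. The SE is 10 × √(1/600 + 1/200) = 0.816, and power is Φ(3/0.816 - 1.96) = 95.7%. With one before and three after it is 88.9%. The stated figure is reproduced, so the same variance components are used below.

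**2. Algebra.** Let X be a baseline covariate, E exposure (0/1), b the effect of X on level, g its effect on change, and δ the true effect.

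- Before Time 0: Y = a + bX + patient effect + error.
- After Time 0: Y = a + bX + gX + δE + patient effect + error.
- Change: gX + δE + error. The term bX has gone.
- Expected interaction coefficient: δ + g × (mean X in users - mean X in non-users).

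If all patients have the same reading times, the interaction is estimated from within-patient contrasts alone. A main effect of X is constant within a patient and cannot alter them.

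**3. Simulation.** There were 40 practices of 100 patients and 40 datasets per scenario, with a true effect of -3 mm Hg. Assumed, not from the protocol: users 0.5 SD higher on X; b = 5 mm Hg per SD; g = -2 mm Hg per SD. The predicted bias in the interaction is 0.5 × -2 = -1 mm Hg. Balanced data gave:

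| Reading of the effect | No covariate | Main effect | Main effect and covariate × period |
|---|---|---|---|
| Exposure × period | -4.01 | -4.01 | -3.00 |
| Contrast of levels after Time 0 | -1.58 | -3.55 | -3.05 |
| Time-varying exposure | -3.68 | -3.95 | -3.00 |

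The second row agrees with arithmetic. Unadjusted, -3 + 0.5 × (5 - 2) = -1.5. The single main-effect coefficient averages 5 and 3, that is 4, so adjusted, -1.5 - 0.5 × 4 = -3.5.

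**4. Unbalanced data.** With about 1.5 readings after Time 0 in non-users and 20 in users, the interaction was -3.91, -3.91 and -2.93. Across the unbalanced scenarios (b of 5 or 10, g of 0 or -2), the main effect moved the interaction by 0.008 to 0.029 mm Hg on average.

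**5. Confounder acting on level only (g = 0), balanced data.** The interaction was unbiased in every model. The main effect took the level contrast from -0.49 to -3.00 and the time-varying estimate from -2.65 to -3.00.

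**6. A second simulation.** This used 6000 patients, 12 replicates, a true effect of 0 and a binary covariate held by 50% of users and 30% of non-users, lowering pressure by 5 mm Hg after Time 0. Predicted bias is 0.20 × -5 = -1.0. Results were -1.04 unadjusted, -1.04 with the main effect and -0.02 with the interaction. The SE rose from 0.29 to 0.30, a ratio of 1.03.

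**The case against.** A reader might infer that the planned adjustment does nothing and that adjusted and unadjusted results must coincide. The documents do not support that. On its plain wording, the 6- and 12-month effect is a contrast of estimated levels, and main effects do adjust levels (steps 3 and 5). If exposure is coded as changing at Time 0, as under Exposures, the main effect moved the estimate by 0.27 to 0.68 mm Hg across scenarios. This part of the objection stands and limits the point to confounding of change. It does not remove it: under both readings, about 0.5 to 1 mm Hg of bias remained in the simulations where the covariate acted on change.

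The term fixed effects does not exclude interactions, since the same section uses it for the exposure interaction, and sections 11.1 and 12.4 allow for a later analysis plan. But the section names its exposure interaction and names none for covariates, so main effects are the natural reading. The model is also stated in full, and a separate plan is only to be considered.

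The protocol has other safeguards: subgroup analyses by sex, age, cardiovascular history, area, deprivation and ethnicity; comparison with practices before implementation; possible matching, raised against regression to the mean; and an acknowledgement of residual confounding. These help in part. Subgroups take one variable at a time and leave the overall estimate as it is, and matching is not a commitment.

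Finally, a bias of 1 mm Hg is not a finding about this study, because no confounder strength is given in the protocol. That stands.

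**Conclusion.** The point holds for the difference-in-differences coefficient. As the model is written, the covariates cannot remove confounding of change in systolic or diastolic pressure, although the same section says that bias from allocation-related variables has to be handled. This is exact in balanced data and holds to within about 0.03 mm Hg in the unbalanced data simulated.

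The size depends on assumed strengths:

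- No effect of the covariate on change: 0.
- 10-point imbalance, -2 mm Hg on change: 0.10 × -2 = -0.2 mm Hg.
- 20-point imbalance, -5 mm Hg on change: 0.20 × -5 = -1.0 mm Hg.

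The last would be a third of the -3 mm Hg design effect and equal to the smaller effect of -1 mm Hg that section 11.2 also considers. The direction could be either way. The protocol is also unclear on whether the 6- and 12-month effect is a contrast of levels or of changes, and that decides what the main effects contribute. The model should be changed before the analysis.

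**What to change.** Replace the covariate sentence with: *Covariates will be included as main effects and as interactions with period (before/after Time 0).* If exposure also interacts with linear time, the covariates need the matching terms. Leave last systolic and diastolic pressure out of the interactions, because they are themselves outcomes from the earlier period. State that the 6- and 12-month effects are the difference-in-differences contrasts from this model.

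The cost is more parameters and a modest loss of precision. The SE rose by about 3% for one binary covariate; the full list, with drug types, doses, frailty items and resource use, would cost somewhat more. The chained-equations imputation in section 12.2 must also be made compatible with the interactions, so that a covariate's relation to pressure may differ by period.

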## Subgroup analysis

Analyses and modelling above will be repeated in the following subgroups:

• Men and women

TM101-A

Protocol Template for a Research Study\_version 15.0CONFIDENTIAL© Copyright: The University of Oxford and Oxford University Hospitals NHS Foundation Trust 2019Page 19 of28

- Age >65 years; >80 years
- Mean SBP before "Time 0" (>160 mm Hg)
- Previous history of myocardial infarction or stroke
- By CCG area
- Users of the system for at least 6months defined as coded data identifying use recorded in the clinical record at both baseline and between months 6-12
- People with baseline blood pressure ≤140/90 compared to those >140/90mmHg
- Deprivation score (High vs Low)
- Ethnicity

Sample size requirements for this study were determined through simulation, as there is little statistical literature for sample size requirements for multilevel modelling. Data was simulated for systolic BP measurements, nested within patients, nested within practices, with the same structure as that detailed in the statistical modelling section. Normal distributions for BP values and variances around patient and practice mean values were assumed (reflecting random intercept terms). A global mean BP of 148 mm Hg was assumed, with practice variation (standard deviation, SD) of 5 mm Hg about this mean. Within a practice, patient variation (SD) was assumed as 17 mm Hg and measurements within a patient were assumed to vary by 10 mm Hg (SD) about the patient mean. The effect of time was assumed to be 0, clinic BP measurements were assumed to be 5 mm Hg higher than home measurements and 25% of patients were expected to take up the Hypertension Plus system.

Assuming an effect size of -3 mm Hg (BP 3 mm Hg lower in patients using the Hypertension Plus system) and a minimum of 4 BP measurements for each patient, 1000 simulated datasets were created and multilevel models as described in the statistical modelling section were fitted to each simulation. This demonstrated that to achieve 90% power at the 5% significance level for the effect of the Hypertension Plus system, 100 patients each drawn from 8 general practices would be required for this study (800 patients in total, 91% power).

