When assuming a smaller effect size (-1 mm Hg) or greater variation (practice SD=10 mm Hg, patient SD = 22 mm Hg or measurement SD = 14 mm Hg), the required sample size was 200 patients from 35 practices, 100 patients from 8 practices, 100 patients from 8 practices or 100 patients from 14 practices respectively. Combining all of these conservative assumptions led to a required sample size 300 patients drawn from 42 practices (12600 patients in total, 90% power).

Assuming an average practice size of 8000 people, a 14% prevalence of hypertension, and an uncontrolled hypertension prevalence of 30%, we expect 336 eligible patients per practice. Considering the scenarios above, that study power is more greatly influenced by the number of practices rather than the number of patients, and the possibility of withdrawal of up to 10% of practices. We anticipate that at least forty and up to approximately sixty practices will contribute, hence adequate power for the comparisons should be available.

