# 12.1. The Level of Statistical Significance

A 5% significance level will be used for all analyses/ tests.

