# 12.3. Potential biases

# (Adapted from Parker et al In Press 2021)

Bias	Issues		Mitigat	tion

(1) Confounding due to non- randomised

	a)	Patients will not be randomised and there is likely to be variation in implementation between practices.	a)	Analysis will take into account area as similar
design	b) c)	Non-participating patients (comparator group) may be systematically different at baseline from those in the telemonitoring group. Practices who take part may be different to those who do not	b) c)	implementation by area Use practices prior to implementation as comparators Within areas
			This is a study s possibi confou taken i	consider ordering effects an observational o there is always the lity of some residual nding that can not be nto account.
(2) Information bias	BP mea differe leading	asured in the clinic and at home may be nt due to white coat and masked effects g to confounding in terms of change in BP .	a)	In a linear mixed model this can be fully adjusted by adding the

The following table summarises key biases and the mitigation we propose.

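### Name general practice as the cluster for the robust variance, and present the simulated powers as conditional on the same effect in every practice

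*Protocol*

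**What the plan says.** Section 11.2 (Statistical modelling) fits multilevel linear models to systolic pressure, with random effects for patient and practice average pressure. Random patient and practice time trends are added only if the likelihood ratio test or AIC favours them. The intervention effect is a fixed exposure-by-time-period interaction. On the variance it says: "To account for autocorrelation between BP measurements in the same individual, standard errors will be estimated using robust methods". It then names the Huber-White sandwich as able to handle within-cluster correlation, without saying what the cluster is.

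Section 12.3, row (1), says "there is likely to be variation in implementation between practices". The mitigation offered is to take area into account, but the model in 11.2 lists no area term. CCG area appears there only as a subgroup.

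The sample-size text, placed under Subgroup analysis, simulates variation around patient and practice means ("reflecting random intercept terms"). It reports 91% power for -3 mm Hg with 8 practices of 100 patients, and 90% for -1 mm Hg with 42 practices of 300 under larger SDs. It concludes that "study power is more greatly influenced by the number of practices rather than the number of patients", and expects forty to about sixty practices.

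**The concern.** A practice random intercept absorbs differences in average pressure between practices. It does not absorb differences between practices in how much the system changes pressure. Users and non-users sit in the same practices, so the intercept largely cancels from the difference-in-differences, whereas a varying effect does not.

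If the effect varies, its average across practices carries an extra variance of τ²/k, where τ is the between-practice SD of the effect and k the number of practices. A sandwich summed over patients does not pick this up; one summed over practices does. The stated reason for the robust errors points to the individual, so an analyst could reasonably cluster there. At stake are the width of the primary interval and the meaning of the stated powers.

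**Working it through.** **Inputs from the protocol.** 5% level (12.1; two-sided assumed, as sidedness is not stated). From the sample-size text: 25% uptake, at least 4 readings per patient, within-patient SD 10 mm Hg (14 in the conservative scenario), 8 x 100 for -3 mm Hg with 91% power, 42 x 300 for -1 mm Hg with 90% power, and 40-60 practices expected. **Assumed:** τ = 0.5, 1 or 2 mm Hg, since no value is given.

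**1. The stated powers.** The timing of readings and the clinic/home mix are not given. With two readings before and two after Time 0:
- 8 x 100: SE = √[100 × (1/200 + 1/600)] = 0.816; power = Φ(3/0.816 − 1.96) = 95.7%.
- 42 x 300: SE = √[196 × (1/3150 + 1/9450)] = 0.288; power = Φ(1/0.288 − 1.96) = 93.5%.

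With readings at random times over ±12 months and more home readings among users after Time 0 (75% v 25%), generalised least squares gives 92.1% and 89.7%. These are close to the stated figures, and both assume τ = 0.

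**2. Power if the effect varies.** To avoid depending on an assumed layout, take the SE implied by each stated power, then add τ²/k.
- 8 x 100: SE₀ = 3/(1.960 + 1.341) = 0.909; SE = √(0.826 + τ²/8).
- 42 x 300: SE₀ = 1/(1.960 + 1.282) = 0.308; SE = √(0.0952 + τ²/42).

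| τ (mm Hg) | 8 x 100, -3 | 42 x 300, -1 |
|---|---|---|
| 0 | 91% | 90% |
| 0.5 | 90% | 88% |
| 1 | 87% | 83% |
| 2 | 74% | 63% |

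For -3 mm Hg with 40 practices of 300, SE₀ = 0.909 × √(800/12000) = 0.235. At τ = 2 the SE is √(0.0551 + 4/40) = 0.394, and power is above 99%. It is still above 99% at τ = 3.

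**3. Coverage of an interval that ignores τ.** Let v be the per-practice variance of the effect estimate. Coverage = 2Φ(1.96 × √[v/(v + τ²)]) − 1. It does not depend on k, because both variance terms shrink as 1/k. With 300 patients per practice and reading SD 10:
- two-before/two-after layout: v = 100 × (1/75 + 1/225) = 1.78, giving 93%, 88% and 72% at τ = 0.5, 1 and 2;
- calibrated to the 91% power: v = 0.826 × 800/300 = 2.20, giving 94%, 90% and 76%.

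A simulation of 40 practices of 300 (300 datasets) agrees. At τ = 2 the mean patient-clustered SE was 0.251 against an empirical SD of 0.391, with coverage 78%. The practice-clustered SE was 0.400, with coverage 95%. At τ = 1 patient-clustered coverage was 91%, within Monte Carlo error of about 1.7 points. At τ = 0 both forms covered 95-96%.

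With the noisier readings of the conservative scenario, v = 0.0952 × 42 = 4.00 and the loss is milder: 94%, 92% and 83%.

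**4. Do the optional practice trends solve it?** In the same simulation, a practice trend shared by users and non-users (SD 2 mm Hg) left patient-clustered coverage at 96%. It is a different source of variation and barely touches the difference-in-differences, so modelling it would not cover a varying effect.

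**5. Do practices drive power in the stated scenarios?** If only total patients mattered, the requirement would scale with (SD/effect)².

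| Change from 8 x 100 = 800 | Expected ratio | Stated ratio |
|---|---|---|
| effect -3 to -1 | 9 | 7000/800 = 8.75 |
| reading SD 10 to 14 | 1.96 | 1400/800 = 1.75 |
| all conservative changes combined | 9 × 1.96 = 17.6 | 12600/800 = 15.75 |
| practice SD 5 to 10 | 1 | 1 |
| patient SD 17 to 22 | 1 | 1 |

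The requirements roughly follow total patients, and doubling the practice SD changes nothing. No two scenarios trade practices against patients at a fixed total, so none can show that practices matter more.

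**The case against.** A reader might infer that the primary intervals will be too narrow and the powers are simply wrong. The documents do not support that, for four reasons.

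- **The cluster is not fixed at the patient.** The reason given concerns the individual, but the unit is left open. In a model with practice random effects, contributions are independent only between practices, so a practice-level sandwich is a natural reading and would cover a varying effect. This stands, and is why the point is conditional.
- **Varying implementation is not a varying effect.** The remark in 12.3 sits in a row about confounding. If the effect is the same everywhere, nothing is lost. At τ = 0.5 mm Hg the power loss is 1-2 points. The value τ = 2 with a mean of -1 mm Hg would, under a normal distribution, mean raised pressure in about 31% of practices.
- **A false-positive rate of 12-30% is tempting but should not be quoted beside these powers.** It comes from 336 patients per practice in the two-before/two-after layout, a different variance basis. On the calibrated SEs the rate at τ = 1-2 is 7-12% (8 x 100) and 8-17% (42 x 300). Even that needs a mean effect of zero with real effects of both signs.
- **The planned study is much larger than eight practices**, and for -3 mm Hg its power is not in doubt.

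It can also be said that the cluster unit belongs in a SAP. Sections 11.1 and 12.4, however, make a SAP optional, and the protocol already states the method and its purpose. The simulation and the remark about practices are protocol content in any case.

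**Conclusion.** The point holds as a conditional one and as a cheap improvement. The plan ties its robust variance to the individual, leaves the cluster unnamed and gives the effect no room to differ by practice. If the variance is then taken at patient level and τ is about 1 mm Hg or more, the primary interval is appreciably too narrow. The size rests on an assumed τ and an assumed layout of readings.

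The stated powers are reproducible, but hold only for a common effect across practices. The qualification matters for the eight-practice minimum and the -1 mm Hg scenario. For -3 mm Hg at the planned size the issue is interval coverage alone.

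The lack of support for the remark about practices and power needs no assumed τ and does not depend on the cluster unit.

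**What to change.** 1. In section 11.2, state that the Huber-White variance is clustered on general practice. With 40-60 practices this performed well in simulation, and it also covers correlation within individuals. A practice-level random exposure-by-period effect is an optional alternative.
2. Describe the 91% and 90% powers as conditional on a common effect across practices, or rerun the simulation with a between-practice SD of the effect of 0.5, 1 and 2 mm Hg and report the results.
3. Correct the sentence on practices and power: either say that the stated scenarios scale with total patients, or support the claim with simulations in which the effect varies by practice.

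The cost is a line of text, a corrected sentence and, if chosen, a rerun of existing code. The downside is possibly wider intervals and slightly less favourable stated power. A practice-level sandwich would be imprecise with only eight practices, but that is not the planned size.

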#### Outcomes

Primary outcome: Systolic blood pressure (SBP) in mm Hg. Blood pressure readings will be extracted from the electronic healthcare record and from the Hypertension Plus system. Readings will be identified as having been taken by a healthcare professional in the clinic or by the patient at home. Readings derived from 24-hour ambulatory BP monitoring will be excluded. Values outside the range 70-250 mm Hg will be excluded. Where multiple readings are recorded on a single day, the lowest value will be selected.

Secondary outcomes:

- Diastolic blood pressure (DBP) in mm Hg, extracted from the electronic healthcare record or the Hypertension Plus system in the same manner as SBP readings. Values outside the range 40-150 mm Hg will be excluded.
- Blood pressure control (binary variable) defined using SBP and DBP readings. Controlled BP will be defined as SBP <140 mm Hg and DBP <90 mm Hg for clinic readings or SBP <135 mm Hg and DBP<85 mm Hg for home readings. Uncontrolled BP will be defined as the presence of any clinic or home SBP or DBP reading above these thresholds.
- Primary care workload defined as the number of face-to-face and telephone consultations where hypertension or hypertension monitoring was listed as the primary problem. Sensitivity analyses will assess whether the addition of BP readings or antihypertensive treatment records to the definition of workload affects these results

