Model assumptions will be checked by producing histograms of residuals and scatter plots of residuals against fitted values. If there is evidence of violation of assumptions, models will be refitted to log-transformations of SBP and DBP and assumptions re-checked.

• Secondary BP control outcome:

For the secondary outcome of BP control, a multilevel logistic regression model will be fitted to the BP control data, using the same steps as described above for the BP outcomes above.

• Primary care workload:

The number of primary care consultations occurring before and after "Time 0" will be totalled separately and modelled using a negative binomial model, including an offset term for person-time of follow-up (to account for potential loss-to-follow-up). This model will include an indicator for time before/ after "Time 0", an indicator for the exposure variable, and an interaction between these variables. Random effects for the patient and practice will also be included and robust standard errors will be estimated similar to other models.

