## 12. Analytical populations

The primary analysis use data from all eligible patients. Analysts will not be blinded to the exposure status. Secondary analysis will be limited to patients in the exposed group who recorded BP measurements through the Hypertension Plus system on more than 3 occasions ("per-protocol" type analysis)

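### A residual-plot check can move the primary SBP and DBP models to the log scale, which changes the difference-in-differences effect from mm Hg to a ratio of ratios

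*Protocol*

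**What the plan says.** All references are to the protocol. Section 11.2 (Outcomes) defines the endpoint on its natural scale: "Primary outcome: Systolic blood pressure (SBP) in mm Hg". Under Statistical modelling, SBP and DBP are fitted by multilevel linear models that include, "to estimate difference-in-differences, interaction terms between the exposure and time period variable (initial model". The reported effect is a contrast at month 6 and at month 12, which the text describes in this way: it "will be estimated by comparing the estimated BP values in the exposed at unexposed groups at these time points, as derived from the models". Huber-White errors are already planned: "standard errors will be estimated using robust methods".

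The check and its consequence follow. "Model assumptions will be checked by producing histograms of residuals and scatter plots of residuals against fitted values". Then: "If there is evidence of violation of assumptions, models will be refitted to log-transformations of SBP and DBP and assumptions re-checked". The text gives no criterion for what counts as evidence, no statement of which fit is primary after a refit, and no route from the log fit back to mm Hg.

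The sample size text, printed under Subgroup analysis, is additive and assumes Normal values in mm Hg: "Assuming an effect size of -3 mm Hg (BP 3 mm Hg lower in patients using the Hypertension Plus system", with a smaller effect of -1 mm Hg as a conservative scenario. Section 12 adds: "Analysts will not be blinded to the exposure status".

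**The concern.** A difference-in-differences estimate does not survive a change of scale. If two groups with different starting levels change by the same number of mm Hg, their trends are parallel in mm Hg but not in log mm Hg. The refit therefore changes both the quantity estimated and the assumption that identifies it.

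The protocol itself allows for the two conditions that make this matter. Section 12.3 says comparators may differ systematically at baseline, and it expects regression to the mean after selection on raised readings. It gives a size for neither.

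At stake is the headline answer, how many mm Hg lower. It could be replaced by a ratio on the strength of a visual check made with the data in hand. There is also little to gain, because the planned robust variance and the expected sample size already protect inference against non-normal or unequal-variance residuals.

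**Working it through.** **1. The design is additive in mm Hg.** Inputs from the sample size text: 8 practices of 100 patients, 25% exposed, at least 4 readings each, practice SD 5, patient SD 17, measurement SD 10, effect -3 mm Hg, 5% level. Assumed here, because the protocol does not state it: readings at random times over the 24 months, half of them in clinic, two-sided test. The mixed model in mm Hg gives SE 0.889, so power = Φ(3/0.889 − 1.96) = Φ(1.41) = 92.1%, against the stated 91%. The planning figure is reproduced on the mm Hg scale.

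**2. What the effect becomes on the log scale.** A fall of 3 at the assumed mean of 148 is the ratio 145/148 = 0.980 (log −0.0205). Applied at other levels, that one ratio means:

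| Level (mm Hg) | Implied effect (mm Hg) |
|---|---|
| 140 | −2.84 |
| 148 | −3.00 |
| 160 | −3.24 |
| 180 | −3.65 |

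A single mm Hg effect no longer exists unless a reference level is fixed.

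**3. Parallel in mm Hg, not parallel in logs.** Starting levels and falls are assumptions, since the protocol gives none. There is no true effect and both groups fall by the same mm Hg, so the additive estimate is 0. With users starting at e, non-users at u and a common fall f:

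log DiD = ln[(e − f)/e] − ln[(u − f)/u], expressed in mm Hg as (exp(log DiD) − 1) × (e − f).

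| Users e | Non-users u | Fall f | log DiD | In mm Hg |
|---|---|---|---|---|
| 155 | 150 | 10 | 0.0023 | +0.33 |
| 158 | 150 | 10 | 0.0036 | +0.54 |
| 160 | 150 | 12 | 0.0054 | +0.80 |
| 150 | 155 | 10 | −0.0023 | −0.32 |
| 150 | 150 | 10 | 0 | 0 |
| 155 | 150 | 0 | 0 | 0 |

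With non-users starting at 148, a gap of only 2 mm Hg and a fall of 10, the result is +0.14 mm Hg, expressed at 148.

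**4. Whether that is visible at the planned size.** The protocol expects 336 eligible patients per practice and 40 to 60 practices: 40 × 336 = 13,440 and 60 × 336 = 20,160. Take 13,440 with 25% exposed (3,360 against 10,080) and assume two readings before and two after. The within-patient change has variance 10²/2 + 10²/2 = 100, so SE = 10 × √(1/3,360 + 1/10,080) = 0.199 mm Hg. Non-users at 148, users 5 higher and a common fall of 10 give +0.35 mm Hg. The chance of a significant interaction with no true effect is about Φ(0.35/0.199 − 1.96) = Φ(−0.20) = 42%. A simulation on the same assumptions gave 41% on the log scale and 5 to 6% in mm Hg. A shift of a few tenths is not lost in sampling error here.

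**5. Whether the log scale buys power.** With 800 patients and two readings on each side, simulated power is 95.5% in mm Hg and 95.4% on the log scale.

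**The case against.** Several points on the other side are fair.

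- **The inputs are not in the protocol.** No baseline gap or common fall is given, and the planning model sets the time effect to 0, where the discrepancy vanishes. Both groups enter by the same rule of above 140/90 (section 8.3), and section 12.3 mentions matching, which may narrow the gap. This stands, so the figures are illustrations.
- **Neither scale is shown to be right.** The table stipulates equal mm Hg falls. If both groups instead fell by the factor 140/150 from 155 and 150, the mm Hg estimate would be off by (155 − 150) × (140/150 − 1) = −0.33. This also stands. It is a reason to fix the scale in advance from the question asked, which here is in mm Hg, and not from residual plots.
- **The rule is a single, named fallback, triggered by diagnostics and not by the effect estimate.** True. A reader might infer from the unblinded analysts that the scale would be chosen for its result, but the text does not support that. The fair criticism is that the trigger is visual, without a criterion.
- **Robust errors do not cure everything.** Residual-versus-fitted plots can show a wrong mean, such as non-linear time, which a sandwich variance leaves in place. This stands and shapes the fix.

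A reader might also infer that the rule is likely to fire, because entry above 140/90 truncates the distribution and digit preference is expected. The documents do not support that. The entry rule concerns only the last reading at baseline, while the model uses all readings over 12 months on each side of Time 0, and heaping need not show as a violation once random effects and covariates are in.

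**Conclusion.** The point holds in limited form. The protocol fixes a data-driven switch of scale for its primary outcome, without saying that the mm Hg fit remains primary or how a log fit is turned back into mm Hg. The switch replaces an additive effect with a ratio of ratios and changes the parallel-trends assumption.

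Under the stated assumptions (no true effect, equal falls of 10 to 12 mm Hg, gaps of 5 to 10 mm Hg) the discrepancy is about 0.3 to 0.8 mm Hg, with a sign that follows the gap. It is a modest part of the -3 mm Hg base case and a large part of the -1 mm Hg scenario. It is zero without a gap or without a common change, and the frequency of the trigger cannot be judged.

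It would go too far to say that the mm Hg effect is irretrievable after a refit. The protocol compares model-estimated BP values, and these could be back-transformed. But that compares geometric means, the mm Hg contrast then depends on the BP level, and the method is unstated.

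**What to change.** Replace the refit sentence with three statements:

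1. The primary SBP and secondary DBP effects are estimated and reported in mm Hg with the planned robust standard errors. Non-normal or unequal-variance residuals do not change the scale.
2. If the plots point to a misspecified mean, for example non-linear time, the mean model is refined on the mm Hg scale.
3. Any log-scale fit is a sensitivity analysis, reported as a ratio, and does not replace the primary estimate.

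The cost is a short edit to section 11.2. No new data are needed, and the stated power is unaffected, because it was computed on the mm Hg scale.
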